4.2. Scientific Rationale for Study Design

Primary endpoint

The primary efficacy measurement is HbA1c, a widely used measure of glycemic control that reflects a cumulative history of glucose levels in the preceding 2 to 3 months.

Overall design

Blinding

This is an open-label study. Investigators, participants, and study-site personnel will be unblinded to the assigned treatment. To eliminate potential biases, designated members of the Lilly study team will remain blinded throughout the study (see Section 6.3). Only a minimum number of Lilly personnel will see the randomization table and treatment assignments before the study is complete.

Study Duration

The treatment duration of 52 weeks is a reasonable time frame to observe the effects of LY3209590 compared to insulin degludec.

The follow-up visit after the last dose is designed to capture any additional safety signals and to monitor the transition from study treatment to non-study diabetic treatment.

Comparator

Insulin degludec was chosen as the comparator because it is widely accepted as the best-in-class basal insulin.

Collection of race and ethnicity data

In this study, collection of demographic information includes ethnicity (where permissible) and race. The scientific rationale is based on the need to assess variable response in safety or efficacy based on race or ethnicity. This question can be answered only if all the relevant data are collected.

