4.3.2. Main analytical approach

The primary objective is to test the hypothesis that LY3209590 is noninferior to insulin degludec on glycemic control in the targeted study population. The noninferiority test will be based on either of the 2 estimands: **treatment regimen estimand** for the US FDA submission and **efficacy estimand** for registrations in other countries. The full significance level of 0.05 will be used for each estimand.

The following table provides the details of treatment regimen estimand and efficacy estimand.

	Treatment Regimen Estimand	Efficacy Estimand
Analysis Population	All participants in EAS1 with non-missing baseline measure	All participants in EAS2 with non-missing baseline measure and at least one non-missing post-baseline scheduled measure
Analysis Data	All non-missing observations at baseline and Week 52 (Visit 31) regardless of the use of study intervention or rescue medications.	All non-missing observations at baseline and all scheduled post-baseline timepoints during treatment period (that is, Weeks 2, 4, 12, 16, 26, 36 and 52) (prior to the date of last study dose + 10 days for LY3209590 (+1 day for degludec), or the initiation of rescue medication whichever is earlier for participants with intercurrent events).
Missing Data	There may be missing values at Week 52 (Visit 31) due to early study discontinuation. The missing values will be imputed using multiple imputation by the retrieved dropout approach. The retrieved dropout participants are those who discontinue study intervention prior to Week 52 but have non-missing measures at Week 52 in the same treatment arm. If there are only a limited number of retrieved participants that leads to a failure in performing the multiple imputation analysis, such as the model cannot converge, or the number of retrieved dropout participants is small (i.e., at least 1 arm has <8 participants who discontinued study treatment early and have endpoint visit measurements), the missing HbA1c at Week 52 will be imputed by return-to-baseline multiple imputation approach (Qu and Dai 2022)	There may be missing values due to the early discontinuation of study intervention or use of rescue medication. The MMRM model will be used, and the missing values will be handled in the MMRM analysis under the assumption of missing at random.

	Treatment Regimen Estimand	Efficacy Estimand

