Analysis Model	
After the imputation, the observed and imputed data will be analyzed by the ANCOVA model using treatment, strata (country, GLP-1 RA treatment at randomization, and SU use at randomization), and baseline value of the dependent variable as independent variables. The statistical inference will be based on the multiple imputation framework by Rubin (1987).
	
The MMRM model will include treatment, strata (country, GLP-1 RA treatment at randomization, and SU use at randomization), visit and treatment-by-visit interaction as fixed effects, and baseline of the dependent variable as a covariate. The Kenward-Roger approximation will be used to estimate denominator degrees of freedom for the MMRM models. An unstructured covariance structure will be used to model the within-participant errors. If this structure fails to converge, the following covariance structures will be used in order until one converges:
 
 1. Toeplitz with heterogeneity 2. autoregressive with heterogeneity 3. compound symmetry with heterogeneous variances 4. Toeplitz 5. Autoregressive 6. compound symmetry without heterogeneous variances.

Abbreviation: ANCOVA = analysis of covariance; MMRM = mixed model repeated measurement.

The 2-sided 95% CI of the LS mean difference (LY3209590 – insulin degludec) in the HbA1c change from baseline to Week 52 (Visit 31) will be estimated. For both estimands, LY3209590 will be declared noninferior to insulin degludec if the upper limit of the 2-side 95% CI for the LS mean difference in the HbA1c (measured in %) change from baseline is below NIM of +0.4%. In addition, the 95% CI for the LS mean difference will be compared to an alternative NIM of +0.3%.

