4.4.1.2. Main analytical approach

The non-inferiority test in change from baseline to Week 52 (Visit 31) in HbA1c for each of the subpopulations with participants using or not using GLP-1 RA will be analyzed. For the treatment regimen estimand (using data from the EAS1), for each subpopulation, the missing data will be imputed by multiple imputation with the approach similar to the imputation used for the primary endpoint. The imputed data for that subpopulation will be analyzed by the ANCOVA model using treatment, strata (country and SU use at randomization), and baseline HbA1c as independent variables. For the efficacy estimand (using data from the EAS2), the MMRM model which includes treatment, strata (country and SU use at randomization), visit and treatment-by-visit interaction as fixed effects, and baseline HbA1c as a covariate will be used, with data from that subpopulation.

The superiority test in change from baseline to Week 52 (Visit 31) in HbA1c will be based on the same primary endpoint analysis described in Section [4.3.2](#).

The time in glucose range between 70 and 180 mg/dL inclusive measured by CGM will be analyzed using an ANCOVA model for treatment regimen estimand and an MMRM model for efficacy estimand. CGM Primary Analysis Population will be used for the analyses. The analyses are similar to the primary analysis described in Section 4.3.2 with additional term of baseline HbA1c stratum ($<8.0\%$, $\geq 8.0\%$) in analysis models. For treatment regimen estimand, only participants with an observation at baseline or at Week 52 will be included in the analysis. the missing data at Week 52 will be imputed by multiple imputation with the approach similar to the imputation used for the primary endpoint. The missing baseline will be imputed using multiple imputation under assumption of missing at random.

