4.9. Changes to Protocol-Planned Analyses

There are no changes but additional details are provided to the analyses described in the protocol.

5. Sample Size Determination

Approximately 888 participants will be randomly assigned to LY3209590 and insulin degludec in a 1:1 ratio. With the assumption of 15% dropout at Week 52, approximately 377 and 377 participants will complete 52 weeks of treatment on LY3209590 and insulin degludec, respectively.

The primary objective of this study is to test the hypothesis that LY3209590 is noninferior to insulin degludec on glycemic control as measured by change from baseline to Week 52 (Visit 31) in HbA1c in participants with T2D who are starting basal insulin for the first time. A total of 754 completers (377 on LY3209590 and 377 on insulin degludec) will provide an at least 99% statistical power to show noninferiority between LY3209590 and insulin degludec using the upper limit of a 2-sided 95% confidence interval (LY3209590 – insulin degludec) and these assumptions:

- a NIM of 0.4%,
- no true difference between treatment groups, and
- an SD of 1.1%.

This sample size also has at least 95% statistical power to show noninferiority between LY3209590 and insulin degludec using a 0.3% NIM at Week 52.

The number of participants in each subpopulation of background treatment will be approximately 50% of the study population with balanced treatment assignment to support the following secondary objectives, controlled for Type 1 error:

- To demonstrate noninferiority of LY3209590 to insulin degludec in HbA1c change from baseline to Week 52 for the subpopulation of participants using GLP-1 RAs; and
- To demonstrate noninferiority of LY3209590 to insulin degludec in HbA1c change from baseline to Week 52 for the subpopulation of participants not using GLP-1 RAs.

In each subpopulation, 188 completers for each study intervention will provide an approximately 90% statistical power to show noninferiority between LY3209590 and insulin degludec using the upper limit of a 2-sided 95% confidence interval (LY3209590 – insulin degludec) and these assumptions:

- a NIM of 0.4%,
- no true difference between treatment groups, and
- an SD of 1.1%.

The 754 completers will provide 95% statistical power to demonstrate the superiority of LY3209590 versus insulin degludec, of change in HbA1c from baseline to 52 weeks, assuming an SD of 1.1% and true mean difference is -0.3%, using the alpha of 0.05.

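### The efficacy-estimand HbA1c MMRM fits one baseline slope to all visits, so the Week 52 contrast can lose part, plausibly most, of the precision gained from baseline adjustment

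*SAP*

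**What the plan says.** SAP 4.3.2 gives two models for the primary endpoint.

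- **Efficacy estimand (registration outside the US).** An MMRM with treatment, strata, "visit and treatment-by-visit interaction as fixed effects, and baseline of the dependent variable as a covariate". Protocol 9.3.2 has the same terms. The visits are "Weeks 2, 4, 12, 16, 26, 36 and 52". On the covariance, the SAP says: "An unstructured covariance structure will be used to model the within-participant errors", with six fallback structures.
- **Treatment regimen estimand (US).** After imputation, "the observed and imputed data will be analyzed by the ANCOVA model", at Week 52 only. That model estimates its own Week 52 baseline slope.

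SAP 4.4.1.2 repeats the MMRM form within each GLP-1 RA subpopulation: "visit and treatment-by-visit interaction as fixed effects, and baseline HbA1c as a covariate will be used". SAP 4.4.2.1 reuses the primary MMRM for HbA1c at Week 26. None of these sections adds a baseline-by-visit term.

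**The concern.** Protocol 4.2 says that HbA1c "reflects a cumulative history of glucose levels in the preceding 2 to 3 months". At Week 2 it is still mostly a pre-treatment measurement, so change should be small, should vary little and should depend only weakly on baseline. By Week 52 both arms have been titrated to one fasting glucose target (Protocol 6.5) from an entry range of 7.0–10.5% (Protocol 5.1). Participants who start higher have further to fall, so change should then depend more strongly on baseline.

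A model with one slope must compromise between these visits. The compromise is a precision-weighted average, and the early visits are likely to be the most precise. If so, the fitted slope sits near the Week 2 value and Week 52 is under-adjusted. At stake is the width of the interval for the non-US primary test and, with less power in reserve, for the two subpopulation noninferiority tests.

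**Working it through.** **Inputs from the documents (SAP Section 5; Protocol 9.5).** 377 completers per arm; 188 completers per arm in each subpopulation; SD 1.1%; "no true difference between treatment groups"; margins 0.4% and 0.3%; 15% dropout.

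**Inputs the documents do not give (assumed).** Baseline HbA1c SD 0.85; slope of change on baseline −0.05 to −0.30 at Week 2 and −0.45 to −0.60 at Week 52; Week 2 residual SD 25–40% of, or equal to, the Week 52 residual SD; total Week 52 SD fixed at 1.1.

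**1. The plan's own figures.** Power = Φ(margin/SE − z), with SE = SD × √(2/n).

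- n = 377: SE = 1.1 × √(2/377) = 0.0801. At 0.4%, Φ(4.99 − 1.96) = 99.9% (stated: at least 99%). At 0.3%, Φ(3.74 − 1.96) = 96.3% (stated: at least 95% "using a 0.3% NIM at Week 52").
- n = 188: SE = 0.1135. At 0.4%, Φ(3.53 − 1.96) = 94.1% at 2-sided α 0.05, and Φ(3.53 − 2.24) = 90.0% at 2-sided α 0.025. The stated figure of about 90% reproduces at 0.025.
- 754/0.85 = 887.1, consistent with 888.

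All these figures reproduce with SD 1.1 and no gain from baseline adjustment.

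**2. What the common slope does.** Let b be the vector of true visit slopes, R the residual covariance given baseline, and σ_B the baseline SD. With complete data and unstructured covariance the fitted slope is

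g = 1′R⁻¹b / 1′R⁻¹1.

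The misfit adds σ_B²(b − g1)(b − g1)′ to the fitted covariance, but the solution for g is the same. Unstructured covariance therefore does not repair the mean model. At Week 52:

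- variance = residual variance + (b₅₂ − g)²σ_B²
- share of the baseline benefit lost = (b₅₂ − g)²/b₅₂².

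When visits are positively correlated, later visits can receive negative weight. Then g can overshoot the Week 2 slope, and the loss can exceed 100%.

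**3. One illustration.** Here baseline SD is 1.0, slopes run from −0.10 to −0.60, residual SD rises about fourfold, and the autoregressive correlation is 0.8. This gives g = −0.06.

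- Residual variance = 1.21 − 0.36 = 0.85 (SD 0.92).
- Common-slope variance = 0.85 + 0.54² = 1.14 (SD 1.07).
- Share lost = 0.2916/0.36 = 81%.
- Power at the 0.3% margin, 377 per arm: 97.1% with the common slope, 99.4% with visit-specific slopes.

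**4. Range with baseline SD 0.85.** For scale, losing the whole benefit (g = 0) raises variance by 1.21/(1.21 − 0.36 × 0.7225) = 1.27 when b₅₂ = −0.60, and by 1.21/(1.21 − 0.2025 × 0.7225) = 1.14 when b₅₂ = −0.45.

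| Week 2 slope | Week 2 residual SD relative to Week 52 | Increase in Week 52 variance |
|---|---|---|
| −0.05 to −0.10 | 25–40% | about 8–34% |
| −0.05 to −0.10 | equal at all visits | about 1–4% |
| −0.30 | either | under about 10% |

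The 34% end needs g of about +0.07, because 0.67² × 0.7225 is about 0.34 × 0.950. In interval width, 8–34% in variance is √1.08 to √1.34, or about 4–16% wider. The ends move by a few points with the assumed correlation between visits.

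**5. Subpopulation tests** (188 completers per arm, margin 0.4%, 2-sided α 0.025, b₅₂ = −0.60, Week 2 slope −0.05 to −0.10).

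- Visit-specific slopes: SD = √0.950 = 0.975, SE 0.1005, power Φ(3.98 − 2.24), about 96%.
- Common slope, variance 34% higher: SD 1.128, SE 0.116, power Φ(3.44 − 2.24), about 88%.
- Common slope, variance 4% higher (equal residual SD): SD 0.994, SE 0.1025, power Φ(3.90 − 2.24), about 95%.

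**6. Check by simulation** (444 randomized per arm, 15% dropout, 200 runs per setting). Week 52 model SEs with no baseline term, a common slope and visit-specific slopes were 0.077, 0.075 and 0.066 when residual SD rose strongly, and 0.079, 0.075 and 0.071 when it rose mildly.

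**The case against.** The strongest reply is that nothing planned is put at risk. The stated power reproduces with SD 1.1 and no baseline gain. With 377 completers per arm and total SD fixed at 1.1, power at the 0.3% margin stayed between 95.5% and 99.7% with the common slope in every scenario examined. A wider interval is conservative for noninferiority. This stands, with one qualification: if 1.1% was meant as the SD after baseline adjustment, power would be lower than stated. The documents do not say which was meant.

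Three stronger readings are tempting, and the documents do not support them.

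- **That most of the adjustment is certainly lost.** The plan gives no visit slopes, baseline SD, residual SDs or correlations. Over all the assumptions tried, the share lost ran from 2% to more than 100%. In the mild simulation setting about half of the reduction in SE was kept.
- **That the treatment estimate is biased.** Treatment is randomized and has its own effect at each visit, so the common slope affects precision.
- **That the US primary analysis is affected.** It is a Week 52 ANCOVA with its own slope.

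A further fair objection is that the single-slope model is also the protocol's, so changing it is more than an edit to SAP wording. That is correct and is allowed for in the fix.

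**Conclusion.** The point holds as a precision issue for the efficacy estimand only. Both documents specify one baseline slope for Weeks 2 to 52, and the covariance structure does not compensate. The slow response of HbA1c makes a weak Week 2 slope and rising residual variance the more natural expectation, so losing most of the benefit is plausible but not established.

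Under the assumptions above, Week 52 variance is about 8–34% higher in that case and about 1–4% higher if residual SD is flat. It is under about 10% higher if the Week 2 slope is already −0.30. For the subpopulation tests this is roughly 88–95% power against 96%. At worst that is within two points of the stated figure, but it gives up power that the collected data could supply. This is a cheap improvement.

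**What to change.** Add a baseline HbA1c-by-visit interaction to the HbA1c MMRMs in SAP 4.3.2 and 4.4.1.2, and to the Week 26 HbA1c MMRM in 4.4.2.1 that reuses the model. Optionally, add the baseline of the dependent variable by visit to the CGM MMRMs; there the covariate is the CGM parameter's own baseline, not HbA1c. Do not apply the term to insulin dose, which has no baseline (SAP 4.1 table). The argument from unstructured covariance also does not carry over to SMBG fasting glucose, which uses compound symmetry.

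The statistical cost is 7 − 1 = 6 degrees of freedom against about 754 completers, with almost nothing lost if the slopes are in fact equal. The procedural cost is a documented departure from Protocol 9.3.2. SAP Section 1 and SAP 4.9 currently declare no changes, so 4.9 must record and justify this one. Under SAP 4.1 the sponsor must also decide whether it alters a principal feature and so needs a protocol amendment. Make the change before unblinding.

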4.3.3. Sensitivity Analysis

4.3.3.1. Two-way Tipping Point Analysis

To confirm the robustness of the primary endpoint results, a 2-way tipping point analysis that represents varying assumptions for missing data from both treatment groups will be conducted. This sensitivity analysis will focus on missing data at the primary endpoint. Penalty parameters for imputed missing values will be added for both treatment arms. The ANCOVA model for treatment regimen estimand will be conducted after penalty parameters are added. The multiple imputation framework by Rubin (1987) will be used to summarize the results.

The corresponding p-value of non-inferiority test will be shown by color scale in the figure.

Additionally, imputation under the noninferiority null hypothesis will be conducted by adding 0.4 (NIM) to the imputed data using treatment regimen estimand (Section 4.3.2) for the LY3209590

group only. The ANCOVA model for treatment regimen estimand will rerun using the adjusted data. The multiple imputation framework by Rubin (1987) will be used to summarize the results.

4.3.3.2. Including Inadvertently Enrolled Participants

The primary efficacy analysis will be repeated for both treatment regimen estimand and efficacy estimand by including inadvertent enrolled participants using mITT population.

4.3.4. Supplementary Analyses

Additional analysis may be conducted as needed.

4.4. Secondary Endpoints Analysis

4.4.1. Key Secondary Endpoints

A graphical approach ([Figure 2.1](#)) will be used to control the overall type I error for the primary objective and test LY3209590 is 1) not inferior to insulin degludec for change in HbA1c from baseline to Week 52 (Visit 31) for the subpopulation of participants using GLP-1 receptor agonists; 2) not inferior to insulin degludec for change in HbA1c from baseline to Week 52 (Visit 31) for the subpopulation of participants not using GLP-1 receptor agonists; 3) superior to insulin degludec for change in HbA1c from baseline to Week 52 (Visit 31); 4) superior to insulin degludec with respect to time in glucose range between 70 and 180 mg/dL inclusive, collected during the CGM collected session prior to Week 52 (Visit 31).

4.4.1.1. Definition of endpoint(s)

See Section [4.3.1](#) for the HbA1c change from baseline to Week 52 (Visit 31).

The time in glucose range between 70 and 180 mg/dL inclusive will be based on the percentage of CGM readings within the glucose range during the specific CGM session. The derivation of CGM parameters is provided in [Appendix 6](#) (Section [6.6](#)).

4.4.1.2. Main analytical approach

The non-inferiority test in change from baseline to Week 52 (Visit 31) in HbA1c for each of the subpopulations with participants using or not using GLP-1 RA will be analyzed. For the treatment regimen estimand (using data from the EAS1), for each subpopulation, the missing data will be imputed by multiple imputation with the approach similar to the imputation used for the primary endpoint. The imputed data for that subpopulation will be analyzed by the ANCOVA model using treatment, strata (country and SU use at randomization), and baseline HbA1c as independent variables. For the efficacy estimand (using data from the EAS2), the MMRM model which includes treatment, strata (country and SU use at randomization), visit and treatment-by-visit interaction as fixed effects, and baseline HbA1c as a covariate will be used, with data from that subpopulation.

The superiority test in change from baseline to Week 52 (Visit 31) in HbA1c will be based on the same primary endpoint analysis described in Section [4.3.2](#).

The time in glucose range between 70 and 180 mg/dL inclusive measured by CGM will be analyzed using an ANCOVA model for treatment regimen estimand and an MMRM model for efficacy estimand. CGM Primary Analysis Population will be used for the analyses. The analyses are similar to the primary analysis described in Section 4.3.2 with additional term of baseline HbA1c stratum ($<8.0\%$, $\geq 8.0\%$) in analysis models. For treatment regimen estimand, only participants with an observation at baseline or at Week 52 will be included in the analysis. the missing data at Week 52 will be imputed by multiple imputation with the approach similar to the imputation used for the primary endpoint. The missing baseline will be imputed using multiple imputation under assumption of missing at random.

